Effect of Medical Marijuana on Neurocognition and Escalation of Use

NCT03224468

Date: 1/28/2022

PARTNERS HUMAN RESEARCH COMMITTEE

DETAILED PROTOCOL: Effect of Medical Marijuana on Neurocognition and Escalation of Use

Protocol #: 2015P001600

Principal Investigator: [name].

Co-Investigator: A. [name]

Summary of Changes Made and Rationale

The IRB protocol, attached, was written for a pilot phase of the trial, and was updated when we received the R01. All measures, outcome definitions, and sample size calculations were up to date in clinicaltrials.gov (NCT03224468). The statistical analysis section was amended before any data were analyzed except for the propensity score analysis for missing data, explained below. No changes were made after looking at the data, except for the propensity score analysis.

Method of randomization:

In Year 1 of the study, we realized that many participants, who were interested in obtaining an MMC never obtained one because of barriers such as expense or needing to go outside the usual healthcare system. We therefore changed our randomization from 1:1 to 2:1 MMC:WLC early in the trial in order to have enough participants in the MMC arm.

Outcomes and outcome definitions:

Outcome measures and definitions were updated on 07/19/2017 in clinicaltrials.gov (NCT03224468), but were not explicitly stated in the IRB protocol.

Primary Outcome Measures:

- Cannabis Use Disorder Symptoms (*Time Frame: Baseline to 12 Weeks*)
 - o The DSM-5 Cannabis Use Disorder Checklist will evaluate symptoms of CUD (number of symptoms).
- Changes in Symptoms of Depression and Anxiety (*Time Frame: Baseline to 12 Weeks*)
 - o For those with depression and anxiety symptoms, the Hospital Anxiety and Depression Scale will be used to assess symptoms.
- Changes in Pain (*Time Frame: Baseline to 12 Weeks*)
 - o For those with pain, the Brief Pain Inventory Severity Scale (BPI-S) will be used to assess levels of pain.
- Changes in Sleep (*Time Frame: Baseline to 12 Weeks*)
 - o For those with insomnia, the Athens Insomnia Scale will be used to assess symptoms.

Secondary Outcome Measures

- o General Medical/Psychiatric Health (*Time Frame: Baseline to 12 Weeks*) The Short Form-12 Health Survey (SF-12) will be used to assess self-report of emotional and physical functioning.
- Cognitive Testing (*Time Frame: Baseline to 12 Weeks*)
 - o Verbal learning/memory, attention, working memory, and complex decision-making will be assessed.

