- Brain-based Measures (*Time Frame: Baseline to 1 Year*)

- Changes in resting state functional connectivity and task-associated activation in brain regions involved in reward, inhibitory control, and working memory will be assessed.

The IRB protocol includes exploratory outcomes that were not presented in this manuscript, but will be included in future publications.

Statistical Analysis: The IRB protocol did not include the final statistical plan. When we brought [name], an experienced clinical trial statistician, on this project in Year 2 of the study, well before any analysis had been conducted, he suggested that instead of a random slopes analysis that assumes the effect of the drug will be to gradually increase the effect or outcome, ie a time x treatment interaction, he suggested we should assume a constant treatment effect over the follow up period, 2 weeks, 1 month, 3 months. [name] also advised us not to adjust for covariates as we originally proposed to do, but to only adjust for baseline symptoms, since randomization should have accounted for differences and we had no strong prior information about what covariates would have an important effect on CUD in people seeking cannabis for medical complaints. [name], without access to the data, made these recommendations to Drs [name] and [name] after which [name], who had access to the data, implemented the analyses.

Propensity score analysis for missing data: We could not ensure that participants in the MMC condition obtained an MMJ card, and we could not give participants a MMJ card because of state and hospitals regulations, a stated limitation of the study. Thus, we conducted a post hoc sensitivity analysis to verify the positive findings of the primary analysis in the final stages of the analysis when we realized that there was a problem with differential drop-out between the randomization and the baseline visit in the MMC and WLC groups.

Sample size calculation:

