This was not included in the trial protocol but calculated for the R01 grant submission in 2016. We aimed to recruit 200 participants in order to have sufficient power to detect benefits and risks of MMCs. To identify a difference in development of CUD symptoms in the MMC vs WLC groups, assuming that the mean number of symptoms for MMC would be .4 (corresponding to 20% of subjects developing CUD) versus .1 in WLC (corresponding to 5% of subjects developing CUD), at a two-sided 0.05 significance level, power was 85%. To identify a difference in symptoms of pain, insomnia, depression, and anxiety, assuming a clinically significant effect would be a 30% reduction in presenting medical symptom with MMC while WLC subjects were expected to have a minimal change, assumed to be a 5% reduction, at a two-sided 0.05 significance level, based on effect sizes in the literature, power was 84% (pain), 90% (insomnia), and 84% (depression and anxiety), with sample sizes of approximately 1/3 (33 in each group) in the pain, insomnia, and anxiety/depression subgroups.

PARTNERS HUMAN RESEARCH COMMITTEE

DETAILED PROTOCOL: Effect of Medical Marijuana on Neurocognition and Escalation of Use

Protocol #: 2015P001600

Principal Investigator: [name].

Co-Investigator: A. [name]

Version Date: 04/15/2020

I. BACKGROUND AND SIGNIFICANCE

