Power/Sample Size. Aim 1 seeks to address the development of CUD (dependent on the number of symptoms reported) in the MM compared with the WLC group. To assess this, we will use the DSM-5 criteria for CUD, which combines the DSM-IV categories of abuse and dependence into a single disorder measured on a continuum from mild to severe. We have based power sample size requirements on the between and within subject ANOVA of the dependent variable of CUD symptoms, comparing the MM versus WLC conditions tested across the baseline to 3 month periods, where the primary effect of interest is the condition X time interaction. A power analysis using the Gpower computer program²⁹ indicated that a sample of 80 participants per group would be needed to detect small to medium effect (Cohen's $d=.3$) with 90% power using a t test with alpha at .05.

Data Analysis Plan: In general, 3 analytic approaches will be employed, corresponding to three types of comparisons and data:

(a) Numeric Data Assessed at Baseline, 3 Months, 6 Months and 1 year. Measures of addiction, tolerance, and cognitive performance will be analyzed with a between- and within-subject analysis of covariance, the primary between-subject factor being Condition, i.e., the active MM vs. WLC group, and the within-subject factor being time, i.e., assessments at baseline and 3 months. Relevant subject-level numeric covariates (i.e. THC metabolite levels) and categorical factors (e.g. disease category) crossed with condition and possibly interacting with time will be included in the analysis. Covariates such as baseline MJ use, primary disorder for which MM is sought, age, and gender will be of interest. The term of primary interest will be the interaction of condition x time as a test of the hypothesis that assignment to the MM condition will be associated with an increased rate of CUD. A limited amount of backward elimination of nonsignificant ancillary terms will be employed to increase power for effects of more interest (e.g. non-significant terms can be dropped from the models). An additional, analogous repeated-measure ANCOVA, restricted to the MM group, will include the third

assessment at 6 months. The Greenhouse-Geisser adjustment for correlated error will be employed for significance tests with more than one degree of freedom. For all models, residuals will be checked graphically for adherence to assumptions of normality and homoscedasticity, and data transformations applied if needed.

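### The 90% power stated for 80 per group at d = 0.3 does not follow from the named t test, which gives 47% two-sided or 60% one-sided

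*Combined protocol and SAP*

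**What the plan says.** The protocol body (version dated 04/15/2020), under Analytic Plan, Power/Sample Size, reports a G*Power result for cannabis use disorder (CUD) symptoms: "a sample of 80 participants per group would be needed to detect small to medium effect", given as Cohen's d = 0.3, "with 90% power using a t test with alpha at .05". It does not say whether the test is one- or two-sided, which standard deviation d refers to, or what within-subject correlation was used.

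The same paragraph describes the basis differently: "We have based power sample size requirements on the between and within subject ANOVA", with the condition-by-time interaction as the effect of interest. Data Analysis Plan (a) then describes that analysis with "the within-subject factor being time, i.e., assessments at baseline and 3 months".

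The Summary of Changes Made and Rationale at the front of the document gives context. It says "The IRB protocol, attached, was written for a pilot phase of the trial, and was updated when we received the R01", and that "The IRB protocol did not include the final statistical plan". It also reports a separate calculation behind a recruitment aim of 200 participants (85% power for CUD symptoms, two-sided 0.05), and says of it: "This was not included in the trial protocol but calculated for the R01 grant submission in 2016". It neither mentions nor withdraws the 80-per-group figure.

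**The concern.** The sentence names everything a two-group t test calculation needs except sidedness: group size, standardised effect, alpha and power. A standardised effect of 0.3 is small, and 80 per group is far too few for 90% power on a plain comparison of two means.

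This is the protocol body's only power statement for the CUD primary outcome. A reader would take it that 80 per group is enough to detect d = 0.3, when the named test needs about three times that number.

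**Working it through.** **Inputs.** From the Power/Sample Size paragraph: n = 80 per group, d = 0.3, alpha = 0.05, t test, stated power 90%. Sidedness is not given, so both are shown. No dropout is stated and none is applied.

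**1. The named test on the stated inputs.** Noncentral t with df = 80 + 80 − 2 = 158 and noncentrality d·√(n₁n₂/(n₁+n₂)) = 0.3·√(6400/160) = 0.3·√40 = 1.897.

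- Power: 0.4705 two-sided, 0.5965 one-sided, against 0.90 stated.
- n per group for 90%: 235 two-sided (power 0.9007; 234 gives 0.8994), 191 one-sided (0.9000; 190 gives 0.8987). 235/80 = 2.9.
- d for 90% at 80 per group: 0.52 two-sided, 0.46 one-sided.

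**2. A paired t test.** This does not compare groups, but it is another t test G*Power offers. With n = 80 and d = 0.3, power is 0.755 two-sided and 0.845 one-sided; 90% needs 119 or 97. No t test on the stated inputs reaches 90% at 80.

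**3. The condition-by-time basis with two assessments.** With two groups and the two times named in Data Analysis Plan (a), the interaction test is the two-group t test on change scores.

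- If d is in SDs of change, step 1 applies unchanged: 47% two-sided, whatever the correlation.
- If d is in raw SDs, the effective d is d/√(2(1−ρ)) for a change score, or d/√(1−ρ²) for ANCOVA, where ρ is the baseline-to-3-month correlation. The documents do not give ρ, so the table shows an assumed range, not an estimate.

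| Assumed ρ | Change score, two-sided | ANCOVA, two-sided |
|---|---|---|
| 0.3 | 36% | 51% |
| 0.5 | 47% | 59% |
| 0.7 | 68% | 75% |
| 0.8 | 85% | 88% |

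90% needs ρ of about 0.83 (change score) or 0.81 (ANCOVA); one-sided, about 0.79 or 0.76.

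**4. d entered as Cohen's f.** Suppose f = d/2 = 0.15 was put into the repeated-measures interaction F test, with noncentrality λ = f²·N·m/(1−ρ), where N = 160 and m is the number of assessments.

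- m = 2: λ = 0.0225·160·2/(1−ρ) = 7.2/(1−ρ). Power is 0.76 at ρ = 0, 0.890 at ρ = 0.30 and 0.90 at ρ = 0.323. With two times, f = 0.15 means a difference in change of 4·0.15 = 0.6 SD, twice the stated d. Check: 0.6/√(2(1−0.323)) = 0.516, the same effective d that step 1 requires.
- m = 4, ρ = 0: λ = 0.0225·160·4 = 14.4 and power is 0.902. At N = 158 it is 0.898.

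**The case against.** The strongest reply is that the sample size may be a correct answer to a different, mislabelled calculation. The paragraph says the sizing rests on an interaction, and the schedule of measures has the CUD checklist at baseline, two weeks, one month and three months: four assessments in that window. The two assessments come from the general analysis paragraph, not from the power sentence. With f = 0.15, four assessments and zero correlation, 160 in total is the smallest balanced sample that reaches 90%. This may well be where 80 came from. It does not rescue the sentence, because it replaces the t test with an F test, reads d as f, and relies on a number of assessments and a correlation that the power sentence does not state. It does mean one cannot say that no calculation gives 80.

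A second reply is that the calculation has been overtaken. The Summary of Changes says the body lacked the final statistical plan, replaces the time-by-treatment analysis with a constant treatment effect adjusted for baseline symptoms, and gives its own power figures. That lowers the stakes, but the sentence stands unmarked in a body said to have been updated on receipt of the grant.

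Third, no practical harm is shown. That stands. Study Procedures plans 200 per group, where the same t test at d = 0.3 has 84.9% power two-sided and 91.1% one-sided. The Summary's aim of 200 in total, split 2:1 (133/67), would give 51.3% two-sided, but that aim rests on different effect assumptions.

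**Conclusion.** The concern holds. From its own inputs the stated 90% is wrong: the named test gives 47% two-sided or 60% one-sided, and 90% needs 235 (191 one-sided) per group, or d of about 0.52 (0.46). These figures assume only equal groups and an independent two-sample t test.

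Every route found to 90% at 80 per group adds an input the paragraph does not give, and the F-test routes also change the test and the effect measure. The correlation results depend on values absent from the documents and show only what would have to be assumed.

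The finding is limited to a stated figure that cannot be reproduced. It does not establish that the trial had 47% power or was too small. It should be corrected, but it does not alter the design.

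**What to change.** In the Power/Sample Size paragraph, do one of the following.

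1. State the sidedness, the SD scale of d, the number of assessments and the within-subject correlation that produced 90%, and correct the effect size and test label to match.
2. If those inputs cannot be documented, restate the figure for the named test: *With 80 participants per group, a two-sided two-group t test at alpha .05 has 47% power for d = 0.3 and 90% power for d = 0.52.* This describes a plain t test, neither the interaction analysis nor the later baseline-adjusted one, and it makes a choice of sidedness that the paragraph leaves open. It is therefore the fallback.
3. Mark the sentence as superseded by the sample size calculation and the analysis described in the Summary of Changes.

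The cost is wording only: no extra participants and no change to the analysis. The stated figure may become less favourable.

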Cannabis is the most commonly used illicit substance in the United States, particularly among young people, and prevalence estimates are steadily increasing¹. Recent estimates suggest that 52% of 18 to 25 year olds have ever tried cannabis², and 23.4% of high school students reporting use one or more times per month³. Delta-9-tetrahydrocannabinol (THC), the psychoactive compound in cannabis, binds to endogenous cannabinoid CB1 receptors located in brain regions such as the hippocampus, amygdala, basal ganglia, prefrontal cortex, substantia nigra and globus pallidus^{4,5}, making frontal-limbic neurocircuitry particularly susceptible to cannabis-related effects in the brain⁶. There is now a well-established relationship between regular cannabis use and a range of potentially adverse outcomes, including effects of learning and cognition (see^{7,8} for review), effects on brain structure and function (see⁹ for review), and potential impacts on mental health⁽¹⁰⁾. Furthermore, regular cannabis use can lead to the development of cannabis abuse or dependence^[11,12], particularly among daily users, where it is estimated that between 25-50% of users will develop a substance use disorder⁽¹³⁾. A recent study found that younger age of onset of regular and maximum daily use were correlated with lower achievement scores and worse neurocognitive functioning¹⁴.

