dose/frequency, type of maintenance medication use (e.g. reduction/discontinuation in opiate use) also with real time, daily diaries. We will also examine whether or not MM patients experience loss of control over intake of marijuana or other substances. We will use measures such as development of tolerance, escalation of use, marijuana caving, and assess experience of reinforcing effects (e.g. euphoria or 'high'), and withdrawal among those who choose to stop using marijuana.

Any changes throughout 12 months in perception of disease symptomatology or in use of maintenance medication will be compared to the waitlist control group.

Aim 2: To assess neurocognitive and psychiatric effects of MM. We expect that neurocognitive outcomes, such as working memory, attention, executive function, anhedonia, amotivation, and decision-making, (when not acutely intoxicated) may be worsened with MM use. Outcomes may be worse in those who use more frequently/heavily (as measured by quantitative THC screens and dosing dairies).

Aim 3: In a subset of patients, assess how MM effects neurocircuitry of prefrontal function. We will use functional MRI tasks to assess working memory, inhibitory control, sustained attention, and risk/reward task performance and brain activation patterns. We expect that individuals who use MM may experience changes from baseline in neurocircuitry involved in memory, attention, inhibitory control and reward.

Aim 4: To assess how medical marijuana patients compare to healthy controls in structural and functional brain imaging measures. We will use functional MRI tasks to assess memory, inhibitory control, sustained attention, and risk/reward task performance and brain activation patterns. We expect that individuals who use MM to show alterations in task-related brain activity.

III. PARTICIPANT SELECTION

Medical Marijuana Participants

Inclusion Criteria:

1. Men and women aged 18-65 years, inclusive;
2. Competent and willing to provide written informed consent;
3. Desire to use medical marijuana for self-reported pain, sleep, or affective (mood and/or anxiety including PTSD) symptoms.
4. Not in possession of a medical marijuana card, but expressing intent to get one.
5. Able to communicate in English language.

Exclusion Criteria:

1. Current daily marijuana use (prior to enrollment)

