2. Current substance use disorders (e.g. cocaine, opiate, stimulant). Light to moderate alcohol use is permitted (defined as 16 or less on the AUDIT), and nicotine dependence is permitted because of the high co-use of nicotine and marijuana. Participants cannot meet current SCID criteria for a use disorder on any illicit substance.
3. Pregnant (verified by a urine test).
4. Diagnosis of acute coronary syndrome, coronary thrombosis, myocardial infarction, cardiomyopathies and arrhythmias such as atrial fibrillation, ventricular tachycardia or fibrillation, thrombophilia such as Factor V Leiden, Prothrombin 20210, antithrombin deficiency, Antiphospholipid syndrome.
5. History of deep vein thrombosis (DVT), pulmonary embolism, stroke.
6. In the opinion of the investigator, not able to safely participate in this study because of any medical or psychological issues (e.g. psychosis) that might compromise their safety.

Healthy Control Participants

Inclusion Criteria:

1. Men and women aged 18-65 years, inclusive
2. Competent and willing to provide written informed consent
3. Able to communicate in English language
4. No contraindications for fMRI (see MRI safety screening form).

Exclusion Criteria:

1. Current or past history of major medical illness by self-report
2. History of diabetes, cardiovascular disease, HIV, Hepatitis C, migraines, head injury or prolonged unconsciousness (> 24 hours)
3. Current use of drugs/medications, such as analgesics
4. Current use of illicit drugs, verified with urine drug screen
5. Pregnancy, verified with urine screen
6. Meets DSM-5 criteria for psychological disorders (current)
7. Reports using marijuana in the past 3 months
8. Reports using marijuana approximately > 50 times in their lifetime
9. In the opinion of the investigator, not able to safely participate in this study.

Healthy Control Participants and Medical Marijuana Participants to Undergo MRI Scanning

Additional Inclusion Criteria for MRI studies (applicable for only the subset who will undergo neuroimaging)

1. Randomized to active MM group or scanned as healthy control participants.

Additional Exclusion criteria for MRI studies (applicable for only the subset who will undergo neuroimaging)

1. Known claustrophobia
2. Presence of electrically, magnetically, or mechanically activated implants (such as cardiac pacemakers) or intracerebral vascular clips
3. History of working with metal (e.g. shavings or fragments could be lodged in scalp or eye)

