When participants in the active study group receive their medical marijuana card, they will be scheduled for a baseline assessment in which they will undergo cognitive testing, interviews, questionnaires, and possibly an MRI scan (see Measures below). In contrast, participants in the waitlist control group will be scheduled for the baseline visit approximately 3-4 weeks following the screening visit. All participants will then be scheduled for repeat assessments at approximately 2 weeks, 1 month, 3 months, 6 months and 1 year after the baseline visit. All participants will receive monthly check in phone calls from a research coordinator at approximately 2, 4, 5, 7-11 months past baseline in order to update study staff on medication changes, recent substance use, and overall physical and mental health. Participants will also be asked to complete a 2-year follow-up phone call, which is identical to previous check in calls, with the addition of the CGI and CUD checklist. If participants are in the active study group, we will ask that they not use MM on the day of testing (though they can use it after testing on that day). These visits will take approximately 3 hours to complete.

In consultation with their prescribing physician, participants in the waitlist control group will be asked to wait to start using MM until they have completed Visit 5 (Three Months). During those 3 months, they will be assessed at the same time points as those in the active MM group (see study schema). After the 3-month waitlist period, the waitlist control group will have the option to start using MM. If this group fails to adhere to the waitlist control, they will be kept in the study and will be asked to complete the same assessment schedule as those initially assigned to the active study group. All participants will be assessed after 1 year.

Measure	Instrument	Visit 1	Visit 2	Visit 3	Visit 4	Visit 5	Visit 6	Visit 7
		Screen	Baseline	Two Weeks	One Month	Three Months	Six Months	One Year
General Medical/Psychiatric Health								
Medical History/ CON MEDS		x	x	x	x	x	x	x
Quantitative cannabinoids			x	x	x	x	x	x
Drug Screen/pregnancy		x	x	x	x	x	x	x
Psychiatric Interview	MINI 7 + Past SUD and AUD	x						x
Suicidality and Health Risk Taking	CHRT	x	x	x	x	x	x	x
Emotional and physical Functioning	SF-12		x	x	x	x	x	x
ADHD symptoms	ASRS		x					x
Impulsivity	BIS-11		x			x	x	x
Executive function	BRIEF		x			x	x	x
Risk perceptions and behavior	DOSPERT		x			x		

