Family history of Addiction	KSADS	x						
Provider Expectations for Recovery Scale	PERS	x						
Substance Use								
Frequency of substance use	TLFB (MJ, EtOH, tobacco, other drugs)	x	x	x	x	x	x	x

Cannabis Use Disorder Screen	DSM-5 Cannabis Use Disorder Checklist	x	x	x	x	x	x	x
MJ craving	MCQ-SF		x	x	x	x	x	x
Marijuana Motives	MMM					x		
Marijuana Withdrawal (if stop)	CWS		x	x		x	x	x
MJ use severity	CUDIT		x	x	x	x	x	x
Harmful drinking	AUDIT	x				x	x	x
Alcohol consumption urge	URGE		x	x	x	x	x	x
Expectancy of MMJ effects	MMEEQ	x	x		x	x	x	x
Reflection of MMJ effects (qualitative)							x	x
Symptoms								
Pain level	BPI	x	x	x	x	x	x	x
Pain Catastrophizing Scale	PCS	x	x	x	x	x	x	x
Perceived Stress Scale	PSS	x	x	x	x	x	x	x
Clinician's Severity Scale	CGI		x	x	x	x	x	x
Insomnia	AIS	x	x	x	x	x	x	x
Anxiety Scale	HADS	x	x	x	x	x	x	x
Delusions and Psychosis	PDI		x		x	x	x	x
Difficulties due to health conditions	WHODAS	x	x			x	x	x
Post-traumatic stress symptoms	PCL	x						x
COVID-19 Specific Questionnaires								
Remote Pre-Visit Form	PVF	x	x	x	x	x	x	x
Effects of COVID-19 pandemic on mood, pain, sleep, lifestyle	COVID Impact	x	x	x	x	x	x	x
Impact of epidemic/pandemic on various areas of life	EPII	x						
Changes in substance use since COVID-19 pandemic	Covid19-CSU	x						
Cognitive Testing								
Verbal learning/memory, attention, working memory, and complex decision-making	CANTAB		x		x	x	x	x
Intelligence / reading	WTAR	x						
MRI Scan								
MPRAGE	Structural		x					x
Resting state	Functional connectivity		x					x
Task-based (i.e. working memory, inhibitory control)	Task-based fMRI		x					x

Drug Testing: At all study visits, participants will provide a urine sample, which will be used to qualitatively screen for cannabis use as well as other substances of abuse. For participants who provide written consent for sample shipment, urine samples will be shipped to quantitatively screen for amount of THC metabolites in urine. Samples will only be shipped for participants who report recent marijuana use and/or qualitatively screen positive for THC. An alcohol reading may also be taken if there is any concern about a participant being intoxicated.

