(b) Daily Numeric Data Collected via Dosing Diaries in the First 3 Months. Daily-recorded numeric measures such as dose and frequency of use of MJ, of analgesic, anxiolytic, and/or antidepressant medications, and ratings of pain, sleep, mood, and anxiety will be analyzed as dependent variables in separate analyses. Preliminary exploratory graphical analyses will be conducted using longitudinal “spaghetti plots” in order to check any need for curvilinear models, explore any clusters of trajectories, and address distribution problems such as floors/ceilings, non-normality, outliers, etc. Analysis methods employed will be mixed fixed and random effects longitudinal models. Fixed terms will be Condition (MM vs. WLC groups) and various relevant crossed factors and numeric covariates. Correlated random terms will be subjects’ intercepts and linear rate of change of their trajectories on the dependent variable across days (curvilinear terms will be included if warranted). In order to test the predictive relation of some of the time-varying variables (e.g., frequency of MJ use) on others (e.g., pain recordings or use of analgesic, anxiolytic, and/or antidepressant medications), the former will be included as additional time-varying predictors in models otherwise analogous to those above. Exploratory structural equation models (SEM) and cross correlations of time series will be examined for evidence of underlying causal dynamics. Cross-lagged partial correlations can be used to test direction of effects.

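### Psychosis (PDI) and suicidality (CHRT) scales are collected in both arms to month 3, but neither has a specified between-arm analysis

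*Combined protocol and SAP*

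**What the plan says.** **Aims and background.** Specific Aims includes "Aim 2: To assess neurocognitive and psychiatric effects of MM". The effects it goes on to list are cognitive domains plus anhedonia and amotivation; psychosis and suicidality are not among them. The background refers to "potential impacts on mental health", and exclusion criterion 6 for the medical marijuana participants concerns "medical or psychological issues (e.g. psychosis) that might compromise their safety".

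**Collection.** The visit schedule under Study Procedures has a row for "Delusions and Psychosis" (PDI) and one for "Suicidality and Health Risk Taking" (CHRT). Of the waitlist arm (WLC) it says: "During those 3 months, they will be assessed at the same time points as those in the active MM group (see study schema". After month 3 that arm may start medical marijuana.

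**Analysis.** The Data Analysis Plan sets out three approaches. For visit data, (a) states: "Measures of addiction, tolerance, and cognitive performance will be analyzed with a between- and within-subject analysis of covariance". For diary data, (b) states: "ratings of pain, sleep, mood, and anxiety will be analyzed as dependent variables in separate analyses". Approach (c) is imaging.

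**Later changes.** The Summary of Changes lists CUD symptoms, HADS, BPI-S and the Athens Insomnia Scale as primary, and SF-12, cognition and brain measures as secondary. It replaces the time-by-treatment model with a constant effect over 2 weeks, 1 month and 3 months, adjusted for baseline symptoms. It says that exploratory outcomes were left out of the manuscript and will be published later, without naming them.

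**The concern.** The trial repeatedly measures two psychiatric harms in both randomised arms, under an aim that covers psychiatric effects, but does not say how either will be compared. The Sample size calculation in the Summary of Changes gives detecting both benefits and risks as the reason for the recruitment target. On these two scales the main report would be silent. The randomised comparison ends at month 3, when the waitlist arm may start, so later follow-up cannot supply the missing contrast.

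**Working it through.** No stated figure is in dispute. The check sets the schedule against every place where an analysis could be specified.

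**Step 1: what is collected up to month 3 (Study Procedures, visit schedule)**

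| Scale | Screen (Visit 1) | Baseline | 2 weeks | 1 month | 3 months |
|---|---|---|---|---|---|
| PDI | no | yes | no | yes | yes |
| CHRT | yes | yes | yes | yes | yes |

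After the baseline visit, PDI has two values in the randomised period and CHRT has three.

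**Step 2: where an analysis could be specified**

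| Place | What it covers | PDI or CHRT? |
|---|---|---|
| Primary outcomes | CUD symptoms, HADS, BPI-S, Athens Insomnia Scale | no |
| Secondary outcomes | SF-12, cognition, brain measures | no |
| Revised model | constant effect, baseline-adjusted | not mentioned |
| Approach (a) | addiction, tolerance, cognition | no |
| Approach (b) | daily diary measures | no |
| Approach (c) | imaging | no |
| Exploratory outcomes | deferred, measures not named | no method given |
| Remuneration; Risks and Discomforts; Monitoring and Quality Assurance | adverse events recorded at check-in calls; individual handling of suicidality; reports to the ethics committee and NIH | no arm comparison described |

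Planned between-arm estimates: 0 of 2 scales. HADS and SF-12 do not fill the gap. HADS is specified for depression and anxiety in those with such symptoms, and SF-12 for general emotional and physical functioning.

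**Step 3: what a comparison could show (context only)**

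The plan gives no SD or expected effect for either scale, so the results are in SD units. Assumptions: two-sided alpha 0.05, 80% power, no loss, no baseline adjustment, one follow-up value.

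SE = sqrt(1/n1 + 1/n2); detectable d = (1.960 + 0.842) × SE; 95% half-width = 1.960 × SE.

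- 200 in total at 2:1 (133:67): SE = 0.150, d = 0.42, half-width 0.29 SD.
- 200 in total at 1:1 (100:100): SE = 0.141, d = 0.40, half-width 0.28 SD.
- 200 per group, as Study Procedures states: SE = 0.100, d = 0.28, half-width 0.20 SD.

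Allocation began at 1:1 and moved to 2:1 early, so with 200 in total the figure lies between 0.40 and 0.42. Baseline adjustment and repeated visits would lower it; losses would raise it.

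For a yes/no definition of worsening, zero events in 133 would give a one-sided 95% upper bound of 1 − 0.05^(1/133) = 2.2%.

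**The case against.** Several points on the other side have force.

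- **The sentence quoted from approach (a) belongs to the older plan.** The Summary of Changes says the IRB protocol did not contain the final statistical plan, and that sentence also omits HADS, BPI and the insomnia scale. Its silence alone proves little. But those three scales were picked up in the primary outcome list, and PDI and CHRT were not. Nor can approach (a)'s time factor of baseline and 3 months be held against the plan, because the revised model uses all three follow-up visits.
- **The scales may be deferred, not dropped.** This stands. A reader might infer that these harms would never be reported; the documents do not support that. What they support is that no analysis is specified and that exploratory outcomes are kept out of the main manuscript.
- **Other harms are planned for.** This also stands. CUD symptoms are the first primary outcome, and cognition, which Aim 2 expects may worsen, is secondary. A reader might infer that the plan reports benefits only, or is tilted towards a favourable result; its outcome list does not bear that out.
- **CHRT may be a safety screen.** It also appears on the healthy controls' screening schedule, and Aim 2 names neither psychosis nor suicidality. But screening does not explain repeating CHRT at every visit, or PDI at 1 and 3 months, in both arms.
- **Adverse events have their own route.** They do, but no comparison by arm is described.
- **Power is modest.** True, which favours intervals over tests; it does not justify leaving the comparison out.

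**Conclusion.** The point holds as a gap in the specified analysis: two harm scales, collected in both arms through month 3 under an aim that covers them, have no planned between-arm estimate. The main report would be incomplete on psychotic-like and suicidal symptoms. The documents do not show in which direction, if any, this would change its conclusions.

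A reader might also infer that the three-month comparison is free of confounding. The documents contradict that. The Summary of Changes reports differential drop-out between randomisation and the baseline visit. Randomisation takes place at Visit 1. CHRT is measured there, before the loss; PDI is first measured at the baseline visit, after it. Month 3 is therefore the end of the randomised comparison, but not of one fully protected by randomisation, and PDI is the more exposed scale.

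The detectable differences (about d = 0.40 to 0.42 with 200 in total, 0.28 with 200 per group) rest on an unadjusted comparison without loss. They show feasibility for moderate effects only. This should be changed, but it does not undermine the primary analyses.

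**What to change.** 1. Name PDI and CHRT as safety outcomes for the baseline-to-12-week comparison, and report them with the primary results.
2. For each, give the difference between the medical marijuana card arm (MMC) and WLC with a 95% CI, from the repeated-measures, baseline-adjusted model already adopted for the primary outcomes. Use all follow-up visits to month 3: months 1 and 3 for PDI; week 2 and months 1 and 3 for CHRT.
3. Use Visit 1 as the CHRT baseline, because it precedes the differential drop-out. This shows and adjusts for the starting level, but does not restore missing follow-up.
4. State that PDI has no Visit 1 value, so its comparison is exposed to that drop-out.
5. Report the proportion with new or worsened symptoms only under a threshold fixed before tabulation. The documents give none for either scale.
6. Label the results as safety estimates without a multiplicity claim, and as post hoc if added after analysis. Do not read a non-significant difference as evidence of safety.

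The cost is SAP wording, agreement on a threshold if proportions are wanted, and two extra tables from data already scheduled for collection. No visits or participants are added. The drawback is wide intervals, especially for rare events.
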